Cover Page

Positional Release Therapy and Therapeutic Massage Reduce Muscle Trigger and Tender Points

NCT #: Not yet assigned

Todays date: 1/14/2021

Study protocol and statistical analysis plan

INTRODUCTION

[figure not shown]
Myofascial pain is a common disorder affecting individuals across the general population and in specific populations, such as athletes, resulting in compromised function, performance, and productivity (Muller et al., 2014). It has been associated with many pain conditions including tension-type headache, spine disorder, and neck and shoulder pain (Muller et al., 2014; Simons & Travell, 1981). Myofascial pain characteristically results from hyperirritable nodules of muscle (trigger points or tender points) associated with pain in affected regions of the body (Jafri, 2014). These areas within the muscle are subjected to continued contraction of muscle fibers due to “too much” calcium resulting in compromised oxygenation of the muscle tissue (Dommerholt et al., 2006). These hyperirritable nodules often occur in fatigued muscles that are subjected to imbalanced postural positions, such as the forward head and rounded shoulders postures (JG & SH, 1983). It can also occur from repetitive movements commonly seen in athletics, and individuals performing manual work (Borg-Stein & Simons, 2002).

Positional release therapy (PRT) and therapeutic massage (TM) are methods used to treat trigger or tender points (D'Ambrogio & Roth, 1997; Knight & Draper, 2013; Wong, 2012). Separate studies on each method have shown efficacy in reducing pain (Aboodarda et al., 2015; Mohammadi Kojidi et al., 2016) muscle tightness (Kelencz et al., 2011) and improving joint mobility (D'Ambrogio & Roth, 1997). PRT is a manual therapeutic technique that first locates tender points within a muscle. Once identified, the practitioner places the muscle in a passively shortened position, while applying slight pressure (D'Ambrogio & Roth, 1997). TM involves the manipulation of soft tissue using techniques such as effleurage and petrissage, to restore blood flow and oxygenation of the muscle tissue (Tessier, 2005; Yang et al., 2012).

Various methods have previously been used to find and assess severity of tender or trigger points. Among those commonly used are the pressure pain algometer with pressure pain threshold (PPT), range of motion electromyography and visual analog scales (VAS) (Aboodarda et al., 2015; Buttagat et al., 2012; Draper, 2015; Ghanbari et al., 2012; Kelencz et al., 2011; Nagrale et al., 2010; Simons & Travell, 1981; Sweety et al., 2014; Wong, 2012). Some studies have also utilized B-mode (two-dimensional) ultrasound imaging (US) to locate, define, trace, and quantify myofascial trigger points after palpation providing a useful means of quantification (Cojocaru MC, 2015; Kumbhare DA, 2016; Muller et al., 2014). Shear wave elastography ultrasound (SWE) has been used to calculate the elastic modulus (tissue stiffness) of muscle reliably, (Brandenburg et al., 2014; Eby et al., 2013; Gennisson et al., 2010; Kumbhare DA, 2016; Muller et al., 2014), but has not been used to quantify changes within trigger points following treatment.

Objectives

The purpose of our study was to quantify the effectiveness of PRT or TM at reducing pain, trigger point tenderness, and muscle stiffness in the upper trapezius muscle by using a combination of the visual analog scale, PPT, B-mode US and SWE to assess changes within trigger points.

METHODS

Participants

We recruited 60 healthy Participants, 24 males and 36 females, (age=27.1±8.8 years, wt=75.2±17.9 kg, ht= 172.8±9.7 cm) to participate in the study. Many of the participants participated on a University dance team. Participants admitted into the study were required to

have upper trapezius pain, during palpation, of at least 10 mm on the 100mm visual analog scale and muscle tightness with an accompanying trigger point in their upper trapezius. Participants who had suffered an acute injury to their upper trapezius in the last 6 days, were undergoing current treatment for their upper trapezius, or were unable to lie on their stomach for an extended amount of time were removed from the study.

The study was approved by the university's Institutional Review Board (IRB#17411) before participant recruitment. All participants provided written informed consent before individual data collection began.

Instruments

We used a GE LOGIC S8 ultrasound machine (4MDMedical, Lakewood, NJ) with the 9L soundhead to measure muscle thickness and stiffness. Muscle thickness was measured using B-mode ultrasound and SWE measured stiffness of the tissue.

In order to quantify subjective perception of pain we used PPT algometer (Jtech Medical Commander Echo pressure algometer, Jtech Medical, Midvale, UT) with a $.5 \text{ cm}^2$ applicator tip along with the 100 mm visual analog scale.

Procedures

Figure 1 outlines study procedures. During the first visit participants underwent screening for presence of inclusion and exclusion criteria as well as palpation for trigger points, following guidelines by Simons, Travell and Speicher (Simons & Travell, 1981; Speicher, 2016). Each side was examined and pain produced during palpation was measured with previously published methods using the VAS (Crichton, 2001). The side that was to be treated was determined by the higher VAS score. Trigger point location, found through palpation, was marked so that all measurements were taken in the same location. All baseline measurements were taken

according to the methods listed below. The participants were then randomly assigned into one of two treatment groups, one being positional release therapy, the other therapeutic massage.

The same order of measurement was used for all participants since we felt that pressure from the PPT algometer could act as a treatment and influence the visual analog scale or elastography measures. Measurements were taken at rest with the participant in prone position, with their arms at their sides for all measurement series, before and after treatment.

[figure not shown]
Pain Pressure Threshold

Pain pressure threshold was determined by a digital pressure algometer on the same point identified during screening. The area was measured once by pressing perpendicularly into the trigger point until the subject declared it to be painful. The peak force measured was then recorded in kg.

Ultrasound and Elastography

The ultrasound machine with a 9L sound head was used to measure two different variables of muscle tension; 1) muscle thickness (B-mode) and tissue stiffness via SWE over the same spot found and marked during screening. Using B-mode on the ultrasound machine, two images aligned with the muscle fibers obtain were taken to obtain muscle thickness. Internal software was used to measure muscle thickness and the 2 images were averaged and recorded in cm. The elastography measure used a 3 cm^2 box positioned over the area containing the trigger point. Nine sample circles of .5cm diameter were set within the box side by side in rows in order to cover as much of the box as possible (shown in figure 1). (source?) Each circle registered a strain modulus reading in kPa. The average of the 9 sample circles was used to represent the stiffness of the muscle in the data

analysis.

Treatment groups

Therapeutic Massage

Participants in the TM treatment group received a timed massage for 5 minutes by the same experienced research. A combination of effleurage and petrissage techniques were used in an organized pattern. Treatment started with effleurage (1-1.5 minutes) and proceeded to petrissage (2.5 to 3 minutes) again followed by effleurage (1 minute) over the marked area of the trigger point, but also in some surrounding areas. The pressure applied by the researcher progressed throughout the massage into the petrissage phase as tolerated by the participant and

pressure was then reduced during the final effleurage phase. After the treatment was completed, the same dependent variable measurements were taken.

Positional Release Therapy

Participants in the PRT group received three successive treatments or releases in the marked area. The researcher located the marked trigger point and while maintaining contact, a light pressure with the clinician's fingertip was applied creating slight dimpling of the skin and blanching of the clinician's fingernail bed. Following palpation, the researcher moved the participant's shoulder into passive abduction and scapular upward rotation and retraction until a position of comfort was achieved with no pain reported by the participant, as directed by Speicher, "Clinical Guide to Positional Release Therapy" (Speicher, 2016) (Figure 3). The participant was instructed to remain completely relaxed during the 90 second treatment. After the recommended 90 seconds had passed the limb was returned to the starting position. This was repeated immediately 2 more times in tender points immediately adjacent to the first one, as recommended by Speicher (Speicher, 2016). Following treatment, the same dependent variable measurements were taken.

Posttreatment measurements

Each participant returned 48 hours post treatment, where dependent measurements were taken. Participants were also given an activity survey to record the number of hours they exercised between the last session and the current session to note any abnormalities or increase in normal exercise. The mark made from the first session, over the examined trigger point, was still visible at the second visit for all participants and was used to determine the location for performing dependent measurements.

Statistical Analysis

A mixed-models analysis of variance was performed for each of the dependent variables (VAS, US, elastography, and PPT). The covariates considered in the analysis were the participants' sex, side of treatment, height, weight, and age. A step-wise regression was used to determine significant covariates for each of the dependent variables. Following the step-wise regression the primary variables of interest, treatment and time of measurement were added along with their interaction for each of the dependent variables. Post hoc t-tests were used to evaluate differences in the measurements. All analyses were performed using SAS, version 9.4 (Chapel Hill, North Carolina) and alpha was set at $p < 0.05$.

References

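### The title says both therapies reduce trigger and tender points, but only the PRT-minus-TM difference is randomised, so the conclusion should be limited to that difference

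*Combined protocol and SAP*

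**What the plan says.** All places are in the combined protocol and SAP.

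- **Cover page, title:** "Positional Release Therapy and Therapeutic Massage Reduce Muscle Trigger and Tender Points".
- **Objectives:** "The purpose of our study was to quantify the effectiveness of PRT or TM at reducing pain, trigger point tenderness, and muscle stiffness". No PRT-versus-TM comparison is named.
- **Introduction:** prior evidence is cited: "Separate studies on each method have shown efficacy in reducing pain".
- **Procedures, allocation:** participants were "randomly assigned into one of two treatment groups, one being positional release therapy, the other therapeutic massage". No sham, untreated or waiting group is described.
- **Procedures, measurement order:** the order was fixed because the authors thought that pressing with the algometer might itself be therapeutic and affect the other readings.
- **Statistical Analysis:** a mixed model with treatment, time and their interaction is fitted for VAS, ultrasound thickness, elastography and pressure pain threshold (PPT). Post hoc t-tests follow, without saying which means they compare. No term is named as the one that answers the objective.

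For VAS, three further statements matter. Entry requires participants to "have upper trapezius pain, during palpation, of at least 10 mm on the 100mm visual analog scale" (Participants). In Procedures, "The side that was to be treated was determined by the higher VAS score". Later in the same section, after side selection, "All baseline measurements were taken", and the resting prone position is specified "with their arms at their sides for all measurement series, before and after treatment". The method descriptions that follow cover PPT and ultrasound but give none for VAS.

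**The concern.** The title and the objective concern what each therapy does. The randomisation addresses only how the two differ. A PRT-minus-TM difference is the same whether both work equally well or neither works, so it cannot support the word used in the title. That conclusion would have to come from the time effect or from within-arm t-tests, which are before-after comparisons without a control.

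Such comparisons include expectation, natural change over 48 hours and the effect of being measured repeatedly. The plan itself recognises the last of these. Its fixed order protects readings within a series, but it cannot undo carry-over from the baseline algometer press to the later series.

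At stake is the main published claim: a change shared by both arms, whatever its cause, could be reported as evidence that both therapies work.

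**Working it through.** The plan gives no sample-size calculation, so there is no figure to reproduce.

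**Inputs.** From the documents: 60 participants, two arms, four outcomes, readings at baseline, immediately after treatment and at 48 hours, alpha 0.05. Assumed: 30 per arm, two-sided tests, equal SD at each time, baseline-to-follow-up correlation r = 0.5 or 0.7.

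**1. Non-treatment shift that reaches p < 0.05**, in SDs of the change score:
- one arm: t(0.975, 29)/√30 = 2.045/5.477 = 0.37
- all 60: t(0.975, 58)/√60 = 2.002/7.746 = 0.26

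**2. Zero treatment effect and a shared shift of 0.3 outcome SD.** The SD of change is SD × √(2(1 − r)), which is 1.00 SD (r = 0.5) or 0.775 SD (r = 0.7). The shift is therefore 0.300 or 0.387 SD of change. The one-arm noncentrality is that value × √30 = 1.64 or 2.12. The noncentral t distribution gives:

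| Test | r = 0.5 | r = 0.7 |
|---|---|---|
| One given arm, paired t | 36% | 54% |
| Both arms (one-arm rate squared) | 13% | 29% |
| Baseline to 48 h, all 60 | 63% | 84% |
| Between-arm difference in change | 5% | 5% |

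The last row would also be 5% if both therapies worked equally.

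**3. Precision of the randomised contrast** (95% CI half-width, in outcome SDs):
- change scores: 2.002 × √(2/30) × √(2(1 − r)) = 0.52 or 0.40
- baseline-adjusted: t(0.975, 57) × √(2/30) × √(1 − r²) = 0.45 or 0.37

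The ratio of standard errors is √((1 + r)/2) = 0.866 or 0.922. Adjustment thus gains 13% or 8% in precision; it does not repair an invalid test.

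**4. Why a null difference is not evidence that both work.** With 30 per arm, the standardised difference detectable with 80% power is (1.960 + 0.842) × √(2/30) = 0.72. Power at 0.5 is 49%.

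**5. VAS only, and only if the screening score is the analysed baseline.** Choosing the higher of two noisy readings gives an expected fall of SD × (1 − R)/√(π(1 − ρ)), where R is reliability and ρ the correlation between the observed side scores. With assumed SD 20 mm, R = 0.7 and ρ = 0.5, this is 6/1.253 = 4.8 mm before the 10 mm entry rule is applied.

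A simulation with both rules and zero effect used mean 30 mm, SD 15 to 20, R 0.6 to 0.9 and correlation of the true side scores 0.5 to 0.8:

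| Baseline VAS | Spurious fall | Significant fall in one arm (nominal 2.5%) | Between-arm test |
|---|---|---|---|
| Screening score | 1.2 to 6.7 mm | 16% to 59% | about 5% |
| Re-measured, independent error | about 0 mm | about 2.5% | about 5% |
| Re-measured, half the error variance shared within visit 1 | 0 mm immediately; 0.6 to 3.3 mm at 48 h | 7% to 17% (48 h) | about 5% (baseline-adjusted) |

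A second set of assumptions (mean 35 mm, SD 15 to 25, observed side correlation 0.3 to 0.5) gave 1.0 to 9.0 mm for the first row. The size depends on the inputs; the direction does not.

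**The case against.** An active-comparator design is legitimate, and the Introduction cites earlier efficacy work on each method. The valid contrast is already planned for every outcome. The post hoc t-tests are unspecified, so they may well be between-arm. The documents contain no results or conclusion. All of this stands. It narrows the point to what may be concluded; the model itself is not at fault. Cited efficacy does not turn this trial's before-after change into a treatment effect, and no equivalence margin is given that would let a small difference between arms be read as shared benefit.

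A reader might infer four stronger things, none of which the documents support:

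- *That the objective claims a reduction.* It sets out to quantify effectiveness and asserts no result; only the title does.
- *That the analysed VAS baseline is the selected screening score.* The order of events in Procedures, and the concern there that the algometer could influence VAS, suggest a fresh reading after side selection. The text does not say so outright, and the procedures figure is not available here.
- *That leaving exercise out of the covariates is an error.* Exercise between visits is surveyed to note abnormalities. It occurs after randomisation, so omitting it from the model is defensible.
- *That the percentages describe this trial.* The 0.3 SD shift has no source in the documents. Expectation would act less directly on ultrasound thickness and elastography than on self-report, and natural change has little time to act before the immediate reading.

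**Conclusion.** The point holds as a limit on the conclusion. With two active arms and no sham or untreated group, the trial can show which therapy changed an outcome more; it cannot show that either one works. The title asserts more than that, and the plan does not prevent a time effect or a within-arm test from being used to support it.

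This follows from the design and needs no assumption. The sizes do: significance in 36% to 54% of trials for one arm and 63% to 84% for all 60, under a shared 0.3 SD shift and no effect, are illustrations.

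The VAS baseline is a minor, conditional matter. If the screening score was used, the before-after fall is inflated by about 1 to 7 mm under the main assumed inputs. If VAS was re-measured at the same visit, some bias may remain at 48 hours. The between-arm contrast is unbiased either way, because selection precedes randomisation.

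**What to change.** 1. Base the conclusion on the baseline-adjusted PRT-minus-TM difference with 95% CI for each outcome, immediately after treatment and at 48 hours, and define the post hoc t-tests as these contrasts. Four outcomes at two times make eight contrasts. Unadjusted, eight independent tests would give 1 − 0.95⁸ = 34% for at least one false positive (less if correlated). So either name one outcome and time point as the main contrast, labelled post hoc if chosen after the data were seen, or apply an adjustment such as Holm across the eight.
2. Report within-arm changes as descriptive means with 95% CIs. State that they are not treatment effects, and that a non-significant between-arm difference does not show that both therapies work.
3. Use a neutral comparative title and add the limitation that there was no untreated or sham arm. Keep the original objective on record.
4. State which VAS reading is the analysed baseline. If it is the screening score, say that the before-after VAS change is inflated by regression to the mean. If VAS was re-measured at the same visit, note that some such bias may remain at 48 hours.

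The cost is wording, one clarification and eight adjusted contrasts from data already collected. The downside is the more modest claim: which therapy did better, not that either one works.

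### The higher VAS picks the treated side and VAS is then tested for a fall with no untreated arm, so regression to the mean can pass for a treatment effect

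*Combined protocol and SAP*

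**What the plan says.** Under Participants, people had to "have upper trapezius pain, during palpation, of at least 10 mm on the 100mm visual analog scale". Under Procedures, "Each side was examined and pain produced during palpation was measured with previously published methods using the VAS", and then "The side that was to be treated was determined by the higher VAS score". Participants were randomised to PRT or TM; there is no untreated or sham arm.

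Under Statistical Analysis, VAS is one of four dependent variables in a mixed-models ANOVA. Treatment, time and their interaction are the effects of interest, and post hoc t-tests follow. The covariates considered are sex, age, height, weight and the side treated, chosen step-wise. Baseline VAS is not among them, so the pre-treatment VAS can enter only as a level of time. Follow-up readings are taken straight after treatment and at 48 hours.

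The text does not say which pre-treatment VAS is analysed. After side choice, "All baseline measurements were taken" "according to the methods listed below", but the headings that follow cover only pressure pain threshold (PPT) and ultrasound/elastography. Two remarks suggest a VAS reading after side choice: the measurement order was fixed because "pressure from the PPT algometer could act as a treatment and influence the visual analog scale or elastography measures", and positioning was the same "for all measurement series, before and after treatment". Figure 1, which outlines the procedures, is not shown and may settle the matter.

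**The concern.** The same scale selects the treated side, sets the entry threshold and serves as an outcome. When the higher of two imperfect readings is chosen, its measurement error is positive on average. A later reading on that side does not share the favoured error, so VAS falls without any treatment effect.

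This matters because the claim concerns reduction. The title reads "Positional Release Therapy and Therapeutic Massage Reduce Muscle Trigger and Tender Points", and the stated objective includes reducing pain. With two active arms, only the time effect and within-arm pre-post tests could support that claim for VAS, and these are the exposed tests. The PRT-TM contrast is not affected, because selection precedes randomisation and acts alike in both arms. PPT, muscle thickness and stiffness are not selection variables.

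**Working it through.** The documents give no power calculation, VAS SD or reliability, so there is no figure of theirs to reproduce.

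**Inputs from the documents.** Treated side = higher of two VAS readings; entry at 10 mm or more; 60 participants; two active arms; alpha 0.05; follow-up immediately and at 48 hours.

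**Assumptions.** SD 20 mm per side, mean 35 mm, 30 per arm, two-sided tests, pre-post contrasts among the post hoc t-tests, no treatment effect. Same-side reliability runs from 0.6 to 0.95. Of the error variance, 0, 25 or 50% is shared by all readings on the first visit.

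**Closed form** (sides alike, nothing shared, no entry rule or scale limits):

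- error variance ve = (1 − reliability) × SD²
- side-specific true variance vs = (reliability − observed side correlation) × SD²
- the higher side exceeds the average by √((vs + ve)/π), of which the fraction ve/(vs + ve) is error
- expected fall = ve / √(π(vs + ve))

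With side correlation 0.5, vs + ve = 0.5 × 400 = 200 and √(200π) = 25.07. The fall is 160/25.07 = 6.4 mm at reliability 0.6, 80/25.07 = 3.2 mm at 0.8, and 20/25.07 = 0.8 mm at 0.95.

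**Check on the test.** A separate simulation (mean 40 mm, reliability 0.8, side correlation 0.5) gave a fall of 3.3 mm and an SD of change of 12.2 mm. Pooled, t is about 3.3/(12.2/√60) = 2.10, near the critical value, and 54% of trials rejected. In one arm, t is about 3.3/(12.2/√30) = 1.48, and 31% rejected.

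**Full simulation** (entry rule and 0-100 limits applied; 6,000 trials per cell, 60 cells). Settings: A, sides alike, observed side correlation 0.5; B, sides alike, true-score correlation 0.5; C and D, as B with one side worse by 20 or 30 mm. The nominal rate in the direction of a reduction is 2.5%.

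*Case 1: the selecting score is the baseline.* Null fall at 48 hours, in mm, the same for any shared fraction:

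| Setting | Rel. 0.6 | 0.7 | 0.8 | 0.9 | 0.95 |
|---|---|---|---|---|---|
| A | 6.7 | 5.0 | 3.4 | 1.7 | 0.9 |
| B | 5.6 | 4.4 | 3.1 | 1.6 | 0.8 |
| C | 4.0 | 3.0 | 2.0 | 1.0 | 0.5 |
| D | 2.6 | 1.9 | 1.2 | 0.6 | 0.3 |

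False findings of reduction: 5-88% pooled, 4-59% in one arm of 30. The immediate fall is the same if nothing is shared. It halves at 50% shared: in A, 3.4/2.5/1.7/0.9/0.4 mm with 58/43/31/18/11% pooled; in D, 1.3/0.9/0.6/0.3/0.2 mm with 11/10/7/6/4%.

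*Case 2: a fresh first-visit reading is the baseline.*

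| Test | Shared error | Null fall (mm) | False reduction |
|---|---|---|---|
| Immediate | 0, 25 or 50% | about 0 | 2.2-3.1% |
| 48 hours | 0% | about 0 | 2.0-3.0% |
| 48 hours | 25% | 0.1-1.7 | 3-11% |
| 48 hours | 50% | 0.2-3.3 | 4-31% |

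A two-arm, three-time ANOVA with pooled error, in place of paired tests, gives 48-hour rates of 5-90% in case 1 and 5-37% in case 2 at 50% shared.

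**PRT-TM comparison.** The baseline-adjusted test rejects in 4.7-5.5% of null trials (nominal 5%) with either reading as baseline. The unadjusted change contrast, run on part of the grid, rejects in 4.6-5.7%.

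**The case against.** The strongest objection is that the large rates belong to the reading the text supports less. The order of steps, the fixed-order remark and the positioning sentence all suggest a VAS taken after side choice. The absence of a VAS heading is weak evidence, since VAS measurement is described just before, and the missing figure may resolve it. With a fresh reading and independent errors, every pre-post test is nominal. The 48-hour bias then depends on an assumed shared fraction. Settings A and B also assume that neither side is truly worse; in C and D at reliability 0.8 the fall is 2.0 and 1.2 mm even in case 1.

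These points stand as limits on size. They do not remove the problem: no readable sentence states a second pre-treatment VAS, and a fresh reading protects the 48-hour comparison only if first-visit fluctuation is not shared.

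It is also true that the planned treatment-by-time interaction is already unbiased, so baseline adjustment mainly adds a little precision and handles chance imbalance. The documents do not say which contrasts the post hoc t-tests cover, so reliance on pre-post tests is inferred from the title and objective. Finally, a PRT-TM difference cannot show that either treatment reduces pain. That is a limit of the design, and no analysis of two active arms removes it.

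**Conclusion.** The concern holds. As planned, a fall in VAS over time or within an arm cannot be separated from the effect of having chosen the side on VAS. The bias runs from negligible (0.3 mm, 5% pooled) to large (6.7 mm, 88% pooled) at 48 hours if the selecting score is the baseline. With a fresh baseline it is confined to the 48-hour comparison and runs from nil to 3.3 mm and 31%. The SD, reliability, side correlation and shared error behind these figures are all assumed, and the documents cannot fix the size. This should be corrected before any VAS reduction is claimed. Confidence is medium, because the baseline reading is not identified.

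**What to change.** 1. State which VAS is the analysis baseline. If one was taken at the marked point after side choice and before the algometer, use it, and keep the screening VAS for eligibility and side choice only.
2. In either case, model the immediate and 48-hour VAS as outcomes, with treatment, time and treatment-by-time. Force baseline VAS in as a covariate; do not offer it to the step-wise selection. Base VAS conclusions on the PRT-TM difference, and label the revised model post hoc, since recruitment and follow-up are described as done.
3. Report within-arm VAS change descriptively and name regression to the mean as a possible explanation: at both time points if the selecting score is the baseline, and at 48 hours even with a fresh one.

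The cost is one sentence, one re-run model and some wording; no new data are needed. Precision is not lost: in setting A at reliability 0.6/0.8/0.95 the 48-hour standard error of the PRT-TM difference is 4.0/3.1/1.6 mm adjusted, against 4.3/3.2/1.6 mm for change scores.

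The real price is a narrower claim. With 30 per arm and SD 20 mm (both assumed), the difference detectable with 80% power is (1.96 + 0.84) × 20 × √(1 − r²) × √(2/30), which is 12.5, 10.3 and 8.7 mm for baseline-to-follow-up correlations r of 0.5, 0.7 and 0.8. Finding no difference would not show that both treatments work, or that neither does. Pre-post change would still mix treatment with repeated palpation and natural change.

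### No step masks arm or time point when muscle thickness and stiffness are read, so reader bias cannot be excluded for the only two outcomes that do not rest on participant report

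*Combined protocol and SAP*

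**What the plan says.** The Ultrasound and Elastography section describes two readings at the marked site.

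- **Thickness.** Two images are taken along the muscle fibres, and "Internal software was used to measure muscle thickness and the 2 images were averaged and recorded in cm".
- **Stiffness.** "The elastography measure used a 3 cm^2 box positioned over the area containing the trigger point". Then "Nine sample circles of .5cm diameter were set within the box side by side in rows", and "The average of the 9 sample circles was used to represent the stiffness of the muscle in the data" analysis.

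Procedures fixes the site: "Trigger point location, found through palpation, was marked so that all measurements were taken in the same location". Baseline is measured before randomisation. Measurements are repeated after treatment in each arm: for massage, "After the treatment was completed, the same dependent variable measurements were taken"; for positional release, "Following treatment, the same dependent variable measurements were taken". They are taken once more at 48 hours.

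None of these sections says who acquired or read the images, or whether that person knew the arm or the time point. Masking is not mentioned anywhere in the body of the document; the word blinded occurs only in titles in the reference list.

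Statistical Analysis names treatment, time of measurement and their interaction as the variables of interest for each outcome, followed by post hoc t-tests at 0.05.

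**The concern.** The trial compares two active manual treatments and has no untreated arm. Much of any statement about effectiveness must therefore come from change over time within each arm.

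Of the four outcomes, the visual analog scale (VAS) is the participant's own rating, and the pressure pain threshold (PPT) is reached when the participant declares pain. Participants in hands-on treatments know what they received, so these two cannot readily be protected from expectation. Thickness and stiffness are the only outcomes that could corroborate the pain results independently.

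That corroboration is weaker if the person reading an image can know that it is a post-treatment image and which therapy preceded it. In the workflow as written, nothing prevents this. A small, unintended tendency to read post-treatment images as improved would be indistinguishable from a treatment response.

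**Working it through.** The documents give no SD, reader reliability, correlation or power figure, so there is no planned figure to reproduce. The check has three parts.

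**1. Where reader judgement enters**

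- *Thickness.* Two images are chosen and measured. No rule is given for choosing images or for placing the measurement points, so judgement enters at the reading step.
- *Stiffness, circles.* Take the box as a square of area 3 cm² (the shape is assumed). Its side is √3 = 1.73 cm. Nine 0.5 cm circles in a 3×3 grid span 3 × 0.5 = 1.5 cm. The slack is 1.73 − 1.5 = 0.23 cm in each direction, so the circles are nearly fixed once the box is placed. This agrees with the stated aim of covering as much of the box as possible.
- *Stiffness, box and probe.* Where the box goes and how the probe is held are decided during scanning. Reading coded files later cannot mask those decisions.

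**2. Which tests a drift would affect**

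Let the reader shift post-treatment readings by *b* SD in both arms. The treatment-by-time interaction compares the two changes, (Δ₁ + b) − (Δ₂ + b) = Δ₁ − Δ₂, so the drift cancels. The time effect and the within-arm post hoc tests keep the full *b*. Only a drift that differs between arms reaches the arm comparison.

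**3. Illustrative size**

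Inputs:
- 60 participants (Participants section). A 30/30 split is assumed, because arm sizes are not stated.
- Alpha 0.05 (Statistical Analysis), two-sided assumed.
- Drift *b* = 0.1, 0.2, 0.3 SD of a single measurement, assumed.
- Pre–post correlation *r* = 0.6 to 0.8, assumed.
- No true effect. The rejection rate comes from the noncentral t distribution.

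*Within one arm (paired test, 29 df).* Noncentrality = b / √(2(1 − r)/30). The denominator is √(0.8/30) = 0.163 at r = 0.6 and √(0.4/30) = 0.115 at r = 0.8.

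*Between arms at one time point, raw values (58 df).* Noncentrality = b / √(2/30) = b / 0.258, where *b* is now the difference in drift between arms.

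| b (SD) | Within arm: noncentrality, r = 0.6 / 0.8 | Within arm: false-positive rate | Between arms: noncentrality | Between arms: false-positive rate |
|---|---|---|---|---|
| 0.1 | 0.61 / 0.87 | 9% / 13% | 0.39 | 7% |
| 0.2 | 1.22 / 1.73 | 22% / 39% | 0.77 | 12% |
| 0.3 | 1.84 / 2.60 | 43% / 71% | 1.16 | 21% |

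The time effect pooled over all 60 has a smaller standard error, √(2(1 − r)/60), so it is more exposed: a 0.2 SD drift gives about 40% at r = 0.6 and 67% at r = 0.8.

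**The case against.** The strongest reply is that silence is not evidence. The text does not say that readers knew arm or time point, and Figure 1, which outlines the procedures, could not be seen in the text reviewed. A reader might infer that the images *were* read unmasked. The documents support only that no masking step is described. That part of the reply stands. It does not remove the point, because measurement order, position, site marking, averaging and circle layout are all set out, and a workflow followed as written would let the reader know both.

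A second tempting inference is that thickness and stiffness carry the same expectation bias as the pain ratings. They do not. Neither is a self-report, so bias can enter only through the operator or reader. The marked site, the averaging of two images and the space-filling circle pattern limit that route.

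Third, coded reading is a partial remedy. It does little for stiffness, where the remaining judgement is at acquisition. The documents also do not say that images were stored, and on-machine measurement during the visit would fit the text equally well. This stands and is why the fix is conditional. It would equally be wrong to infer that coded reading makes either outcome free of bias.

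Fourth, the magnitude is hypothetical, and the documents give no reason why a reader would favour one active treatment over the other. Both statements are true. The between-arm column is therefore the less likely scenario, and the weight falls on change over time. A baseline-adjusted arm comparison would be more sensitive to a differential drift, but baseline is not among the listed covariates, so no such figure is used here.

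**Conclusion.** The point holds as a gap in the measurement method that should be closed. As described, the workflow does not protect the reading of thickness and stiffness from knowledge of arm and time point, so reader-related detection bias cannot be excluded. Thickness is the more exposed of the two at the reading step; for stiffness the exposure is mostly box and probe placement.

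The consequence falls on the time effect and the within-arm post hoc tests. The treatment-by-time interaction is safe from a drift common to both arms, though not from one that differs by arm. The rates above show what drifts of 0.1 to 0.3 SD would do; they do not estimate what happened. They depend on the assumed drift, correlation, equal arms and two-sided testing.

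The documents do not support a finding that bias occurred, or that the treatment comparison is invalid. They also do not present protection from expectation as the reason for using SWE: the Introduction's stated reason is that it had not been used to quantify change within trigger points after treatment.

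**What to change.** Add to Ultrasound and Elastography:

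*B-mode images and SWE frames are stored, given random codes that hide participant, arm and time point, and shuffled. After all visits the same reader makes the thickness measurements on the coded files, and sets the nine circles where the stored frames allow. These readings are analysed.*

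The text is in the past tense with recruitment complete, so this wording should be used only if the step is actually carried out:

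- **If images from completed visits were saved,** code and re-read them in this way.
- **If they were not saved,** report thickness and stiffness as not masked, and limit claims about change over time in these outcomes accordingly.
- **In either case,** state who acquired and who read the images and what they knew, and report VAS and PPT as unmasked if they were.

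The cost is a file-coding step and extra reading time. The same reader can do the work, so no additional assessor, participant or visit is required. The limitation to state is that image acquisition, including probe handling and box placement, remains unmasked.
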